3.2 Schedule of Assessments and Procedures

See the Schedule of Assessments in [Appendix Section 19.1](#).

3.2.1 STUDY TREATMENTS

This study will include approximately 36 evaluable patients with TED in 4 treatment arms. Treatment-naïve patients will be randomized (in a 1:1:1 ratio) upon enrollment to LASN01 in either a high-dose (600 mg Q4W ×7-13 doses) or low-dose (300 mg Q4W ×7-13 doses) treatment arm or to placebo. [REDACTED]

[REDACTED] Treatment arms for the randomized and open-label patients are shown in Table 1. The protocol was amended as additional safety data became available to increase the duration of treatment with LASN01.

CONFIDENTIAL

The contents of this document are confidential to [REDACTED]
Unauthorized use, disclosure, or reproduction is strictly prohibited.

Table 1. Multiple Dose Study Design

Randomized Treatment Arm	Dose	Number of Doses	Number of Patients
1	Low-dose LASN01 (300 mg Q4W)	13	8
2	High-dose LASN01 (600 mg Q4W)	13	8
3	Placebo (Q4W)	13	8
Total Number of Patients			24

4. Sample Size

This study will enroll up to 36 evaluable patients with TED across four treatment arms. Approximately 24 patients will be randomized in a 1:1:1 ratio to receive LASN01 600 mg Q4W, LASN01 300 mg Q4W, or placebo.

Randomized Treatment Arms:

- The pooled primary analysis represents a 2:1 randomization of pooled LASN01 (300 mg and 600 mg arms) to placebo with about 24 patients.
- The placebo response rate is assumed to be ~15% (based on Teprotumumab FDA approval data from 2020).
- Assuming a pooled LASN01 response rate of 65% (an absolute treatment effect of 50% over placebo), a sample size of 8 patients per arm provides approximately 81% power at a 10% significance level using a one-sided Fisher's exact test.
- If the placebo response rate is 10%, the power increases to approximately 90% at the same significance level.
- Power calculations were performed using R Version 4.2.1 (R Core Team, 2022), employing simulation methods with 10,000 iterations implemented via the 'statmod' package (Giner, 2016).

CONFIDENTIAL

The contents of this document are confidential to [REDACTED]
Unauthorized use, disclosure, or reproduction is strictly prohibited.

5. Analysis Populations

5.1 Efficacy Population

The Efficacy Population includes all randomized patients who received at least 1 dose of study drug and 1 post-dose primary efficacy assessment, with treatment assignment designated according to randomized treatment.

The efficacy population will be used for all efficacy analyses.

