1.3. Schedule of Activities

Table 1. Schedule of Assessments and Procedures –Treatment Period

Study Procedures	Study Day																
	Screen (Day-30 to Day-1)	1 ^a	8 (±1)	15 (±2)	29 (±3)	43 ^b (±2)	57 (±4)	85 (±4)	113 (±4)	141 (±4)	169 (±4)	197 (±4)	225 (±4)	253 (±4)	281 (±4)	309 (±4)	337 (±4)
	Week	1	2	3	5	7	9	13	17	21	25	29	33	37	41	45	49
Informed consent	X																
Demographics	X																
Inclusion/exclusion criteria evaluation	X	X															
Height (Screening only), BMI evaluation	X	X															
Body Weight	X	X			X		X	X	X	X	X	X	X	X	X	X	X
Medical history	X	X															
Complete physical examination	X																
Brief physical examination		X ^c	X	X	X ^c		X ^c	X ^c	X ^c	X ^c	X ^c	X ^c	X ^c	X ^c	X ^c	X ^c	X ^c
Pregnancy test (WOCBP) ^d	X	X ^a			X		X	X	X	X	X	X	X	X	X	X	X
Follicle-stimulating hormone as applicable ^e	X																
Urine drug screen	X																
Serology (ie, hepatitis B virus surface antigen, hepatitis C virus antibody, HIV-1, and HIV-2)	X																
12-lead ECG	X	X ^f	X		X ^f		X ^f	X ^f	X ^f	X ^f	X ^f	X ^f	X ^f	X ^f	X ^f	X ^f	X ^f
Vital signs ^g	X	X	X	X	X		X	X	X	X	X	X	X	X	X	X	X
CAS ^h	X	X ^a			X		X	X	X	X	X	X	X	X	X	X	X
Proptosis measurement ^v	X	X ^a			X		X	X	X	X	X	X	X	X	X	X	X

Study Procedures	Study Day																
	Screen (Day-30 to Day-1)	1 ^a	8 (±1)	15 (±2)	29 (±3)	43 ^b (±2)	57 (±4)	85 (±4)	113 (±4)	141 (±4)	169 (±4)	197 (±4)	225 (±4)	253 (±4)	281 (±4)	309 (±4)	337 (±4)
	Week	1	2	3	5	7	9	13	17	21	25	29	33	37	41	45	49
Ophthalmic assessments ⁱ	X	X			X		X	X	X	X	X	X	X	X	X	X	X
Visual fields assessment ^j		X			X		X		X		X			X			
Color vision assessment ^k		X			X		X	X	X	X	X	X	X	X	X	X	X
Dilated funduscopy		X										X					
Orbital MRI ^l	X						X	X				X			X		
Randomization ^m		X															
Facial photography ⁿ	X						X	X	X	X	X	X		X		X	
Dose (LASN01 or placebo) administration (observed for 4 hours following first dose)		X			X		X	X	X	X	X	X	X	X	X	X	X
Concomitant medications evaluation	X	X	X	X	X	X	X	X	X	X	X	X	X	X	X	X	X
Adverse event evaluations	X	X	X	X	X	X	X	X	X	X	X	X	X	X	X	X	X
Hematology, coagulation	X	X ⁿ	X	X	X ⁿ		X ⁿ	X ⁿ	X ⁿ	X ⁿ	X ⁿ	X ⁿ	X ⁿ	X ⁿ	X ⁿ	X ⁿ	X ⁿ
Chemistry	X	X ⁿ	X	X	X ⁿ		X ⁿ	X ⁿ	X ⁿ	X ⁿ	X ⁿ	X ⁿ	X ⁿ	X ⁿ	X ⁿ	X ⁿ	X ⁿ
Urinalysis	X	X ⁿ	X	X	X ⁿ		X ⁿ	X ⁿ	X ⁿ	X ⁿ	X ⁿ	X ⁿ	X ⁿ	X ⁿ	X ⁿ	X ⁿ	X ⁿ
Hemoglobin A1c	X									X ⁿ		X ⁿ		X ⁿ			
Thyroid tests (TSH, T3, free T4)	X	X ⁿ			X ⁿ		X ⁿ	X ⁿ	X ⁿ	X ⁿ	X ⁿ	X ⁿ	X ⁿ	X ⁿ	X ⁿ	X ⁿ	X ⁿ

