7.2. Early Discontinuation of Study Intervention

Patients who prematurely discontinue study drug should still remain on study for scheduled visits and assessments and every effort should be made to obtain all protocol-specified assessments to avoid losing data that is needed to evaluate safety and efficacy. The assessments for primary, secondary, and exploratory endpoints, including the MRI and facial photography, should be completed within 30 days of the study drug discontinuation. The reason for premature discontinuation of study drug administration should be recorded on the appropriate page(s) of the eCRF.

Study drug must be discontinued in case of progressing disease posing an unacceptable risk to the patient that requires immediate treatment. In such cases, the PI should contact the Sponsor and the PI and the Sponsor Medical Monitor will discuss and determine whether the patient should continue in the study.

Reasons for withdrawal from study drug may include, but are not limited to:

- Withdrawal of consent
- An AE, which, in the opinion of the PI (or designee), warrants the patient's discontinuation of study drug infusion; in the event of study drug withdrawal due to the occurrence of an AE, the Medical Monitor must be notified within 24 hours
- Non-compliance with study drug administration or other protocol procedures
- Prohibited concomitant medication
- Physician decision
- Pregnancy
- Study termination

A patient who is withdrawn from study drug, or patients who are randomized, but not dosed, for reasons not related to study drug or progression of TED may be replaced at the discretion of the Sponsor.

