9.1. Analysis Sets

Analysis populations are:

- Efficacy Population: all randomized patients who received at least 1 dose of study medication and 1 post-dose primary efficacy assessment, with treatment assignment designated according to randomized treatment.
 - [REDACTED]
- Per-Protocol Population: includes all patients in the Efficacy Analysis Population who complete the treatment and the primary efficacy analysis and do not incur any major protocol violation that would challenge the validity of their data, as defined in the SAP
- Safety Population: all randomized patients who receive ≥ 1 dose of study drug
 - [REDACTED]
- PK Analysis Population: all patients who receive ≥ 1 complete dose of study drug and for which ≥ 1 valid PK parameter can be calculated
- PD Analysis Population: all patients who receive ≥ 1 complete dose of study drug and who have ≥ 1 post-therapy PD assessment

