6.2 Missing or Inconclusive Data Handling

In general, safety data will not be imputed except for missing or partial dates. The early termination visit will be mapped to the closest scheduled week based on study day. If the patient already has a result in the closest scheduled week, then the early termination visit will be mapped to the next nominal week. Missing efficacy data will be imputed using Last Observation Carried Forward (LOCF) to Week 53 (Day 365). Unscheduled visits will not be carried forward; however, the early termination visit that are mapped to the closest nominal week will be carried forward until Week 53 (Day 365).

Every effort will be made to collect all data at specified times. For the SRC or other IAs, selected AE variables that are missing will be re-coded or imputed as the worst option possible. Missing Relationship to Study Treatment will be re-coded as Related.

CONFIDENTIAL

The contents of this document are confidential to [REDACTED]
Unauthorized use, disclosure, or reproduction is strictly prohibited.

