11.1 Analysis of Primary Efficacy Endpoint(s)

The primary efficacy endpoint is the percent of patients showing a response in proptosis measured using Hertel exophthalmometer (≥ 2 mm decrease from baseline) in the study eye and separately in either eye without increased proptosis (≥ 2 mm increase) in the other eye at Week 37 (Day 253) as measured by Hertel Exophthalmometer. The primary efficacy endpoint will be assessed with a one-sided Fisher's exact p-value comparing the pooled active group to placebo at each visit, including the primary endpoint visit at Week 37. Interpretation of statistical significance should be made at the $\alpha=0.1$ level. Two-sided 95% CIs for responder analyses may be calculated with the Clopper-Pearson exact method.

Fisher's exact test syntax:

```
Proc sort data = <data>;
    by TRTPN descending AVALC; *orders the responses;
run;

proc freq data=<data> order=data; *Keeps the order in the dataset;
    tables TRTPN*AVALC / fisher;
run;

where TRTPN is planned treatment (1=Active and 2=Placebo)
```

CONFIDENTIAL

The contents of this document are confidential to [REDACTED]
Unauthorized use, disclosure, or reproduction is strictly prohibited.

AVALC is the responder variable (Y = response in proptosis of ≥ 2 mm decrease from baseline in the study eye and separately in either eye and < 2 mm increase in the other eye; and N = response of < 2 mm decrease from baseline in the study eye and separately in either eye or ≥ 2 mm increase in the other eye).

Note: with the above ordering, the right-sided p-value will be the correct one-sided p-value from Fisher's exact test for the primary hypothesis.

The primary efficacy analysis will utilize the Efficacy Population with LOCF. Additional sensitivity analysis may be conducted on the primary efficacy endpoint with observed data only (ODO) using study eye.

The percentage of proptosis responders by treatment arm (pooled active group and placebo) over time through Week 37 using line graphs for the Efficacy Population with LOCF will be produced for study eye and either eye separately.

Tables and figures will be provided for the individual treatment groups and pooled active group for all available visits while Week 37 remains the primary endpoint.

. A listing of proptosis in both eyes will be provided.

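### A randomised, dosed patient with no post-dose Hertel reading at all is dropped from every efficacy analysis instead of counting as a non-responder, which raises the observed response rate in whichever arm loses the patient

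*SAP*

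**What the plan says.** SAP 5.1 sets two conditions beyond randomisation: "The Efficacy Population includes all randomized patients who received at least 1 dose of study drug and 1 post-dose primary efficacy assessment". Protocol 9.1 uses the same rule ("all randomized patients who received at least 1 dose of study medication and 1 post-dose primary efficacy assessment"), so the SAP inherits it. SAP 5.1 gives the set full scope ("The efficacy population will be used for all efficacy analyses"), and SAP 11.1 applies it to the primary test: "The primary efficacy analysis will utilize the Efficacy Population with LOCF".

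In the schedule (Protocol 1.3) the row "Proptosis measurement" is marked at Screening, Day 1, Day 29 and later dosing visits, but not at Day 8 or Day 15. The first scheduled post-dose reading is therefore at Week 5.

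LOCF to Week 53 is the only imputation rule for efficacy data (SAP 6.2). Two provisions limit who is affected:

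- Proptosis is measured at the EOS/ET visit, and SAP 6.2 uses that reading: "The early termination visit will be mapped to the closest scheduled week based on study day". It is then carried forward.
- Protocol 7.2 keeps patients who only stop study drug on study, with the endpoint assessments due soon after: they "should be completed within 30 days of the study drug discontinuation".

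**The concern.** Membership of the primary analysis set depends on something observed after randomisation, namely whether a post-dose Hertel reading exists. A dosed patient without one is neither a responder nor a non-responder. The patient leaves the 2×2 table. LOCF cannot help, because there is no post-dose value to carry, and the population rule excludes the patient in any case.

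The endpoint is binary, so these patients could be kept without a model: no documented response at Week 37 can be scored as non-response. The plan does not do this in any analysis. The observed-data analyses draw on the same population, and SAP 16 removes both the protocol's sensitivity analysis of the proptosis endpoint and the per-protocol analyses. Nothing planned would show how far the result depends on the exclusion.

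With 16 pooled LASN01 patients against 8 on placebo, one patient is 6.25% of the pooled group or 12.5% of the placebo arm. One or two exclusions can move a borderline result across 0.10.

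**Working it through.** **Inputs.** From SAP 2.2, 4 and 11.1: 16 pooled LASN01 v 8 placebo, response rates 65% v 15% (10% as the alternative placebo rate), one-sided Fisher exact test at 0.10. The number of patients with no post-dose reading is not in the documents; one or two is my assumption. No replacement of lost patients is assumed.

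**Plan's own figure.** For x LASN01 responders of n and y placebo responders of m, the one-sided p is the hypergeometric upper tail: the sum over i ≥ x of C(n,i)·C(m,x+y−i)/C(n+m,x+y). Power is the sum of Bin(x;16,0.65)·Bin(y;8,0.15) over tables with p ≤ 0.10. This gives 81.8% (stated: about 81%). With placebo at 10% it gives 89.7% (stated: about 90%). The plan's power reproduces.

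**Two LASN01 losses, 9 responders among the other 14, placebo 2/8.**

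- Dropped, 9/14 v 2/8: [C(14,9)·C(8,2) + C(14,10)·C(8,1) + C(14,11)] / C(22,11) = (56,056 + 8,008 + 364)/705,432 = 0.0913. Significant.
- Counted as non-responders, 9/16 v 2/8: [C(16,9)·C(8,2) + C(16,10)·C(8,1) + C(16,11)] / C(24,11) = (320,320 + 64,064 + 4,368)/2,496,144 = 0.1557. Not significant.

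The LASN01 rate moves from 9/16 = 56.3% to 9/14 = 64.3%.

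**One placebo loss: the direction reverses.**

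- Counted, 10/16 v 2/8: (224,224 + 34,944 + 1,820)/2,704,156 = 0.0965. Significant.
- Dropped, 10/16 v 2/7: (168,168 + 30,576 + 1,820)/1,352,078 = 0.1483. Not significant.

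**How many tables flip.** With one LASN01 loss only two do: 5 responders v 0/8 (p = 0.1028 counted, 0.0892 dropped) and 13 v 4/8 (0.1340 counted, 0.0814 dropped). With two LASN01 losses, seven do.

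**Chance of a significant result.** The remaining patients respond at 65% v 15%. The power sum is repeated with a LASN01 and b placebo patients lost, taking p from x/(16−a) v y/(8−b) if dropped and from x/16 v y/8 if counted.

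| Patients with no post-dose reading | Dropped | Counted as non-responders | Difference (points) |
|---|---|---|---|
| 1 LASN01 | 76.3% | 75.9% | +0.4 |
| 2 LASN01 | 79.9% | 68.7% | +11.1 |
| 1 placebo | 76.3% | 85.1% | −8.8 |
| 1 in each group | 69.3% | 79.7% | −10.4 |

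(Differences are taken before rounding.) If the true LASN01 rate were 40%, one LASN01 loss gives 30.4% v 25.3% and two give 32.9% v 20.2%.

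**Type I error.** With one to three LASN01 patients dropped and the remaining patients in both groups at a common response rate of 15% or 30%, the attained level is at most 4.5%, under the nominal 10%.

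**The case against.** The strongest reply is that the affected group is narrow. A reader might infer that everyone who leaves before Week 5 is removed. The documents do not support that: a Hertel reading at the early termination visit puts the patient in the set and is carried forward, withdrawing patients are encouraged to attend that visit, and patients who only stop drug are meant to stay on study and be measured. What remains is a dosed patient who leaves within four weeks and gives no reading. The study-withdrawal list in Protocol 7.3 names neither adverse events nor worsening TED, so the documents do not show that such patients are the ones least likely to respond. All of this stands.

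It is also fair that the rule is the protocol's own, in a proof-of-concept study without strong error control. SAP 7 tabulates the analysis populations by arm and lists exclusions with reasons, so a reader could rescore an excluded patient. That gives transparency, but it does not replace a specified analysis.

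The size depends on which losses are chosen. The 11-point gap with two LASN01 losses is partly Fisher discreteness: 14 v 8 happens to have more power (79.9%) than 15 v 8 (76.3%). The consent withdrawals described in SAP 1 and 16 concern re-consent to later protocol versions and the extension, so they are no evidence of losses in the first month.

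A reader might also take the assessment named in SAP 5.1 to mean the Week 37 reading itself, which would exclude many more patients. That does not fit: the primary analysis applies LOCF at Week 37, and would have nothing to impute if every member of the set had a Week 37 reading.

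**Conclusion.** The point holds in a limited form. The plan excludes from every efficacy analysis a randomised, dosed patient with no post-dose Hertel reading at all, and no planned analysis counts that patient as a non-responder. The exclusion raises the observed response rate in the arm that loses the patient. It is not a bias in favour of LASN01 as such: a placebo loss works against LASN01.

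The size depends on a number the documents do not give, and that number may be zero or small. At the planned rates, one LASN01 loss changes the chance of success by 0.4 points, two by 11.1 points in LASN01's favour, and one placebo loss by 8.8 points against it. These figures assume 16 v 8 as planned, no replacement, and remaining patients responding at 65% and 15%. A reader might infer that the rule inflates type I error above 10%; the attained levels calculated here do not show that. The issue is post-randomisation exclusion and the fragility of a borderline result.

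**What to change.** For the proptosis responder analysis, use all randomised patients who received at least one dose, analysed as randomised, and score a patient with no post-dose proptosis reading as a non-responder. Keep the current Efficacy Population for the continuous CAS analyses, which need a post-dose value. If the primary set is to stay as the protocol defines it, add this as a specified sensitivity analysis at a minimum.

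The cost is SAP wording, with no new data. The response rate becomes slightly lower in an arm that loses a patient. Because that can be the placebo arm, the change does not always make the test harder to pass. If no patient lacks a post-dose reading, the results are unchanged.

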5.2 Safety Population

The Safety Population includes all randomized patients who receive at least 1 dose of study drug [REDACTED] who receive at least 1 dose of study drug. The patients will be analyzed as treated. All safety analyses will be based on the Safety Population.

5.3 Pharmacokinetic Population

The PK Population includes all patients who receive at least 1 complete dose of study drug and for which at least 1 valid PK parameter can be calculated. All PK analyses will be based on the PK Population and will be analyzed as treated.

5.4 Pharmacodynamic Population

The PD Population includes all patients who receive at least 1 complete dose of study drug and who have at least 1 post-therapy PD assessment. All PD analyses will be based on the PD Population and will be analyzed as treated.

6. General Statistical Considerations

6.1 Unit of Analysis

The unit of analysis in this study will be the study eye and either eye for all appropriate ophthalmic summaries. The study eye is determined by the PI or designee as the more severely affected eye at Week 1 (Day 1) before dosing. This will be based on the severity of proptosis in both eyes. If both eyes are

CONFIDENTIAL

The contents of this document are confidential to [REDACTED]
Unauthorized use, disclosure, or reproduction is strictly prohibited.

affected equally, the principal investigator (PI) or designee will select the study eye and may take into account other factors such as the CAS. If both proptosis and CAS are equal, the PI or designee will select the study eye and may consider other factors for disease severity per their expert judgement. Both eyes will be assessed for efficacy and safety at designated study visits, but the study eye will be used to assess the primary clinical endpoint. If only one eye is determined to meet the eligibility criteria, that is the study eye by default.

The non-study eye will be referred to as the fellow eye. Fellow eye safety summaries will also be presented as appropriate.

Either eye for responder analyses is defined as the eye that meets responder criteria in either eye (study eye or fellow eye) at Week 37 (Day 253) and the same eye will be analyzed at each visit. If both eyes meet the responder criteria at Week 37 (Day 253) the study eye will be the eye to use in either eye analyses at each visit.

Either eye for continuous Total CAS analyses is defined as the eye that achieves the largest reduction in Total CAS at Week 37 (Day 253), and this single eye will be used for analyses at all visits. If both eyes demonstrate an equal reduction in Total CAS at Week 37 (Day 253), the study eye will be used as the either eye. As a single eye per patient per visit will be analyzed and that eye is held constant for all visits, no additional considerations are needed to account for multiple eyes within a patient.

Non-ocular AEs and medical history will be presented at the patient level.

For ECG and vital sign data that is measured in triplicate, the average of available readings will be the unit of analysis.

6.2 Missing or Inconclusive Data Handling

In general, safety data will not be imputed except for missing or partial dates. The early termination visit will be mapped to the closest scheduled week based on study day. If the patient already has a result in the closest scheduled week, then the early termination visit will be mapped to the next nominal week. Missing efficacy data will be imputed using Last Observation Carried Forward (LOCF) to Week 53 (Day 365). Unscheduled visits will not be carried forward; however, the early termination visit that are mapped to the closest nominal week will be carried forward until Week 53 (Day 365).

Every effort will be made to collect all data at specified times. For the SRC or other IAs, selected AE variables that are missing will be re-coded or imputed as the worst option possible. Missing Relationship to Study Treatment will be re-coded as Related.

CONFIDENTIAL

The contents of this document are confidential to [REDACTED]
Unauthorized use, disclosure, or reproduction is strictly prohibited.

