9.3. Handling of Dropouts and Missing, Unused, and Spurious Data

Every effort will be made to collect all data at specified times. No substitutions will be made for missing data, unless explicitly specified in the SAP.

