QTcF	QT Interval Corrected by Fridericia's Formula
RTF	Rich Text Format
SAP	Statistical Analysis Plan
SD	Standard Deviation
SE	Standard Error
SOC	System Organ Class
SRC	Safety Review Committee
$t_{1/2}$	Terminal half-life
TEAE	Treatment-Emergent Adverse Event
TED	Thyroid Eye Disease
T_{last}	Time point with the last measurable concentration
TLF	Tables, Listings and Figures
T_{max}	Time at which the maximal concentration is observed
TSH	Thyroid Stimulating Hormone
TSI	Thyroid Stimulating Immunoglobulin
V_{ss}	Steady-state volume of distribution
V_z	Volume of distribution based on the terminal phase
WHODrug	World Health Organization Drug Dictionary

CONFIDENTIAL

The contents of this document are confidential to [REDACTED]
 Unauthorized use, disclosure, or reproduction is strictly prohibited.

1. Introduction

This statistical analysis plan (SAP) details the planned analyses and reporting for protocol LASN01-CL-2201, with the United States Version 7.0 dated 15NOV2024, and the European and UK Version 7.1 dated 22NOV2024. The statistical methods herein supersede those in the clinical protocol. Any additional required analyses will be completed and identified in the clinical study report.

This SAP has been prepared with consideration of the latest International Conference on Harmonisation (ICH) E9 Guideline, "Guidance for Industry: Statistical Principles for Clinical Trials," and the latest ICH E3 Guideline, "Guidance for Industry: Structure and Content of Clinical Study Reports."

This study was conducted as proof of concept for evaluation of role of IL-11 in thyroid eye disease (TED). TED trials have assigned a target eye, traditional to trials that deliver drug to one eye. As LASN01 is being administered systemically, there should be no difference between either eye and response in either eye should be considered. Procedurally, the protocol has used the target eye as primary endpoint, however, as the study is signal seeking in nature, the drug is administered systemically (intravenously [IV]), and response in either eye is evaluated in consideration of response. A substantial number of patients did not reconsent to protocol v7.0/7.1, which led to the early termination of the study. Only the primary endpoint (proptosis responder) and total 7-point Clinical Activity Score (CAS; Total CAS) endpoints will be summarized. Other exploratory or secondary endpoints will not be analyzed and the per protocol population has been removed.

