2.2 Statistical Hypotheses

The primary clinical endpoint will be assessed using a one-sided Fisher's exact test at a 0.10 significance level. This analysis combines the 600 mg and 300 mg Q4W treatment arms ("pooled group") and compares them to placebo.

- Null Hypothesis (H_0): At Week 37, the percentage of patients showing a proptosis response in the study eye without deterioration in the fellow eye and separately in either eye is less than or equal in the LASN01 pooled group (300 mg and 600 mg) compared to placebo.
- Alternative Hypothesis (H_1): At Week 37, this percentage is greater in the LASN01 pooled group compared to placebo.

3. Study Design and Procedures

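### The primary Week 37 proptosis responder analysis scores missing outcomes by LOCF and has no rule for readings taken after prohibited TED therapy, so responses not shown to hold at Week 37 could count

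*SAP*

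**What the plan says.** **Imputation.** SAP 6.2: "Missing efficacy data will be imputed using Last Observation Carried Forward (LOCF) to Week 53 (Day 365"). An early termination visit is mapped to a scheduled week and carried forward in the same way; unscheduled visits are not. SAP 11.1: "The primary efficacy analysis will utilize the Efficacy Population with LOCF".

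**Who is scored.** The Efficacy Population (SAP 5.1) needs one dose and one post-dose proptosis reading. The first scheduled post-dose reading is Week 5 (Protocol Table 1).

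**What counts as response.** SAP 11.1 codes a responder from millimetre change in the two eyes and nothing else. Current TED treatments are only listed (SAP 9.1). Protocol 6.8.2 prohibits corticosteroids, teprotumumab, other immunomodulators and orbital surgery, with an exception for medication needed to treat adverse events.

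**Staying in after stopping drug.** Protocol 7.2: "Patients who prematurely discontinue study drug should still remain on study for scheduled visits and assessments". Where drug is stopped for progression that needs immediate treatment, continuation is decided case by case.

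**Missing data.** Protocol 9.3: "No substitutions will be made for missing data, unless explicitly specified in the SAP". SAP Section 1: "A substantial number of patients did not reconsent to protocol v7.0/7.1, which led to the early termination of the study". SAP Section 16 adds that several patients withdrew consent.

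**Checks on the primary result.** SAP 11.1: "Additional sensitivity analysis may be conducted on the primary efficacy endpoint with observed data only (ODO) using study eye". SAP Section 16 lists observed-data analyses as added for every proptosis and CAS table. It also removes the protocol's sensitivity analysis of the proptosis responder rate. It cites Protocol 9.4.2 for this, which I read as the MMRM in 9.2.4.

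**The concern.** The endpoint asks whether a patient has a 2 mm reduction at Week 37. LOCF answers a different question for anyone not measured then: whether the reduction was present at the last reading, up to 32 weeks earlier (Week 37 minus Week 5). It treats an unseen outcome as known and unchanged.

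The responder rule has a second gap. A reduction measured after steroids, another biologic or orbital surgery would be scored as a response to the randomised treatment, because the SAP has no rule for such readings.

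The remaining check covers only part of this. Observed-data-only analysis drops patients without a Week 37 value and still counts readings taken after other therapy.

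The effect reaches beyond one table. SAP 6.1 picks the eye for the either-eye responder analysis by its Week 37 status and keeps that eye at every visit, so a carried-forward value can also decide which eye is analysed.

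**Working it through.** **1. Inputs and the plan's own power.** The test is stated in SAP 2.2: "The primary clinical endpoint will be assessed using a one-sided Fisher's exact test at a 0.10 significance level". SAP Section 4 assumes 65% response on pooled LASN01 and 15% on placebo, and says that "a sample size of 8 patients per arm provides approximately 81% power at a 10% significance level using a one-sided Fisher's exact test".

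Exact power = sum over a = 0..16 and b = 0..8 of Bin(a; 16, 0.65) × Bin(b; 8, 0.15), taken where the one-sided Fisher p is at most 0.10. This gives 81.8% (stated: about 81%). With placebo at 10% it gives 89.7% (stated: about 90%). Both figures reproduce, so the same calculation is used below.

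**2. Where one patient matters.** The one-sided Fisher p is the sum, over k from the observed active count a upward, of C(16,k) × C(8,m−k) / C(24,m), where m is the total number of responders.

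- 8/16 v 1/8, m=9: (102,960 + 11,440) / 1,307,504 = 0.087
- 7/16 v 1/8, m=8: (91,520 + 12,870) / 735,471 = 0.142

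| Significant | p | One patient changed | p |
|---|---|---|---|
| 8/16 v 1/8 | 0.087 | 7/16 v 1/8 | 0.142 |
| 6/16 v 0/8 | 0.059 | 5/16 v 0/8 | 0.103 |
| 9/16 v 1/8 | 0.051 | 9/16 v 2/8 | 0.156 |

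The first two rows show one active response that is carried forward under LOCF but not counted otherwise. The third shows one placebo patient responding under other therapy, which works against the drug.

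**3. How often the boundary is in play.** Under 65% v 15%, the probability of a significant result that would be lost by removing one active response is 10.1% of all outcomes, or 0.101/0.818 = 12.3% of significant ones.

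**4. How LOCF could inflate the result (assumed inputs).** Suppose true Week 37 response is 15% in both arms, a share d of patients is missing, and 65% of the missing active patients had a transient response at their last reading, against 15% on placebo. The apparent active rate is then 0.15(1−d) + 0.65d.

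| d | Apparent active rate | False-positive rate |
|---|---|---|
| 12.5% | 21.3% | 3.2% |
| 25% | 27.5% | 9.0% |
| 37.5% | 33.8% | 18.3% |
| 50% | 40.0% | 30.6% |

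If 50% rather than 65% had a transient response, the rates are 2.2%, 5.1%, 9.8% and 16.2%. With no transient excess the rate is 0.7%. Non-responder counting keeps it at 0.4% or less throughout. The documents give neither d nor the transient rate.

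**5. What non-responder counting costs.** If the same share d is affected in both arms, the rates become 0.65(1−d) and 0.15(1−d).

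| d (assumed) | Active | Placebo | Power |
|---|---|---|---|
| 0 | 65.0% | 15.0% | 81.8% |
| 12.5% | 56.9% | 13.1% | 71.9% |
| 25% | 48.8% | 11.3% | 59.1% |
| 37.5% | 40.6% | 9.4% | 43.6% |
| 50% | 32.5% | 7.5% | 26.8% |

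**The case against.** The protocol lets the SAP specify substitution, and Section 16 discloses LOCF as a change, so no rule was broken or hidden. LOCF applies to both arms and carries non-response as well as response, so its bias has no fixed direction. Any 24-patient trial can turn on one patient at its boundary under any missing-data rule, and at 10/16 v 1/8 (p=0.027) losing one active response leaves p=0.051. Non-responder counting also fills in an unseen outcome. The study is a terminated proof of concept without multiplicity control. All of this stands, and it limits how strongly the point can be put.

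A reader might also infer four stronger things that the documents do not support:

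- **That patients who did not re-consent lack Week 37 data.** Section 16 says they declined a 12-month extension. Protocol 5.1 still refers to a 36-week treatment period, and Protocol 7.2 keeps patients who stop drug in scheduled visits.
- **That patients on the 7-dose version are carried past their own schedule at Week 37.** That version's visit schedule is not in the documents. An observed Week 37 reading after dosing has ended is also not imputed.
- **That patients stopped for progression remain in the study.** Protocol 7.2 leaves this to the investigator and the Medical Monitor.
- **That LOCF was chosen with knowledge of the results.** Section 16 reports that the sponsor's clinical team was unmasked but does not date the LOCF decision, and the CRO statisticians stayed masked until database lock.

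None of this makes LOCF suited to a Week 37 responder endpoint, supplies a rule for readings after prohibited therapy, or settles whether the observed-data check is required.

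**Conclusion.** The point holds as a matter of suitability and should be acted on. The primary analysis can score a reading from as early as Week 5 as a Week 37 outcome. It would also count a reduction after prohibited TED therapy in a patient who stayed in; this second part rests on the SAP's silence together with a millimetre-only definition, not on an explicit statement. The number of patients concerned and the direction of any bias are unknown.

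The effect is potentially decisive only near the boundary, which is about 10% of outcomes under the design assumptions. The false-positive figures show that inflation is possible, but they depend wholly on assumed missingness and on more transient response among missing active patients. With the proptosis MMRM removed and the observed-data check stated inconsistently, the plan does not clearly commit to any check on the primary result.

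**What to change.** 1. For the Week 37 responder analysis, count as a non-responder any patient who has neither a Week 37 assessment nor an early termination visit mapped to Week 37. Do the same for any patient with prohibited TED therapy or orbital surgery before Week 37.
2. Keep LOCF and observed-data-only as mandatory sensitivity analyses. Add a small best/worst-case grid over the patients with no Week 37 value, and report their number by arm.
3. Reconcile SAP 11.1 with Section 16 on whether the observed-data analysis is required and for which eye.
4. Re-run the either-eye tables and figures that depend on Week 37 status.

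The data needed, TED treatments and dosing records, are already collected. The work is SAP wording, the primary table and the dependent either-eye outputs. The real cost is lower response rates in both arms and less power, as tabulated above for assumed shares. The LOCF result stays visible beside the new primary analysis.
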